4 LIST OF ABBREVIATIONS

AE	Adverse Event
AHRF	Acute Hypoxemic Respiratory Failure
APP	Awake Prone Positioning
ARDS	Acute Respiratory Distress Syndrome
BDRM	Blinded Data Review Meeting
CRF	Case Report Form
CSR	Clinical Study Report
DSMB	Data Safety Monitoring Board
FPFV	First Patient First Visit
FU	Follow-Up
GCP	Good Clinical Practice
ICH	International Conference on Harmonisation of Technical Requirements for Registration of Pharmaceuticals for Human Use
ICU	Intensive Care Unit
ISF	Investigator Site File
LPLV	Last Patient Last Visit
MD	Medical Doctor
PI	Principal Investigator
PP	Prone Positioning
SAE	Serious Adverse Event
SAP	Statistical Analysis Plan
SOP	Standard Operating Procedure

5 ETHICS

5.1 Ethics Committee or Institutional Review Board

This study will be planned and performed in accordance with

- The Declaration of Helsinki in its version of Helsinki, 2024;
- The EU Clinical Trial Directive 2001/20/EC;
- The EU Clinical Trial Directive 2001/83/EC
- The "Note for Guidance on Good Clinical Practice" (CPMP/ICH/135/95), and other applicable laws.

5.2 Ethical Conduct of the Study

The Sponsor will submit, among other documents, the study protocol, the patient information and the informed consent form to all involved Ethics Committees and request for approval (favourable opinion). Further the sponsor will provide the clinical trial application. The approval of the Ethics Committee must be obtained prior to the start of any study related intervention.

5.3 Patient Information and Informed Consent

An Investigator will explain to the patients (or legal representative) the nature, significance and implications of the study. He will explain all methods, rules of conduct and any restrictions which may apply. Possible effects and side effects will be discussed. Patients (or legal representatives) will be informed that they are free to withdraw from the study at any time, without giving any reason for doing so. They must be able to understand the full implications of their decision. Study participation will be in consent with the patient or legal representative.

All participants (or legal representatives) will sign an informed consent form as evidence of consent. The patient information sheet and the informed consent form of each participant will be filed in the Investigator Site File (ISF). A second original of the signed consent form and a copy of the information sheet will be handed to the patients after signature and before enrolment.

If a patient is unconscious and not able to be informed/ to provide informed consent and a legal representation status is not established/ available, the inclusion is at the discretion of the local investigator and can be performed under an emergency enrolment strategy. In this case the informed consent process has to be repeated as soon as the patient is awake or a legal representation has been established as deferred consent strategy.

5.4 Confidentiality

The Principal Investigator (PI) of each study site must assure that patients' anonymity will be strictly maintained and that their identities are protected from unauthorised parties. Only an identification code (i.e., consists of identification number, sex and year of birth) should be recorded on any form or biological sample submitted to the laboratory, Sponsor, Competent Authorities' or Ethics Committee. The PI must keep a screening and enrolment log showing codes and names for all patients screened and for all patients enrolled in the trial.

5.5 Publication Policy

The Sponsor represented by Coordinating Principal Investigator will publish the result of this study considering all legal requirements. The trial will be registered at clinicaltrials.gov.

Beside University Medical Centre Hamburg-Eppendorf, as the Sponsor of the study, is committed to the unrestricted and widespread dissemination of all primary and secondary endpoint results. The publication of the principal results from any single-centre experience within the trial is not allowed.

Following analysis and presentation of the primary endpoint results, active and passive participation of all Committee Members, high enrolling Investigators will be solicited for data analysis, abstract and manuscript preparation. Submission of all abstracts and publications regarding the primary and secondary endpoints from the study requires approval by the Coordinating Principal Investigator and his deputy. Final decision regarding authorship lies at the Coordinating Principal Investigator and his deputy.

The sole acquisition of data does not qualify for authorship. All authors must meet each of the following 3 criteria:

1. Substantial contribution to conception and design of study protocol and/or analysis and interpretation of data
2. Drafted the article or revised it critically for important intellectual content
3. Approved the final version for publication.

7 INTRODUCTION AND BACKGROUND

7.1 The Medical Problem

About 10% of admissions to ICUs are associated with acute hypoxemic respiratory failure (AHRF) (1). Early in the disease non-invasive respiratory support modalities (e.g., non-invasive ventilation, high-flow nasal oxygen) are used for improving oxygenation and unload respiratory muscles, thereby reducing inspiratory effort and the risk of patient-self-inflicted lung injury (2). However, some patients are suffering from acute respiratory distress syndrome (ARDS), which is associated with a mortality of up to 45% in the severe category (1). The management of ARDS has made considerable progress both regarding supportive and pharmacologic therapies. Lung protective mechanical ventilation is the cornerstone of ARDS management. Besides that Prone positioning (PP) in patients with moderate to severe ARDS has shown improved oxygenation and benefit regarding mortality (3). The response to prone positioning depends on the redistribution of densities and regional perfusion (4). Guidelines recommend early PP alongside with lung protective ventilatory strategies (5). Adverse events during PP can include endotracheal tube obstruction, pressure sores and loss of venous access (6). Of interest, first reports of PP in ARDS go back to the 1970 where Phiel et al. tested a bed which allowed position changes of up to 180 degrees (7). The first effects of PP were reported in 1977 by Douglas and colleagues (8). Since then, studies have focused mainly on mechanically ventilated patients. Prone position of non-intubated, awake patients with AHRF results in many of the same physiological changes improving oxygenation (9). Awake prone positioning (APP) of patients with acute hypoxemic respiratory failure gained considerable attention during the coronavirus disease 2019 (COVID-19) pandemic (9). With the spread of non-invasive respiratory support strategies in wards and ICUs APP in non-mechanically ventilated patients was often performed and became the focus of several clinical trials (5). Prior to the pandemic, reports of APP were limited to case series in patients with influenza and in immunocompromised patients, with encouraging results in terms of tolerance and oxygenation improvement (9-11). High-quality evidence from randomized controlled trials (RCT) derived from studies enrolling only COVID-19 patients (12-15). In a Meta-Trial including six RCTs APP of patients with acute hypoxemic respiratory failure due to COVID-19 reduced the incidence of treatment failure and the need for intubation without any signal of harm (14). A recent RCT showed that prolonged APP (target > 12 h daily for 7 days) reduces the intubation rate without significant harm (12). The most recent ESICM Guideline on acute respiratory distress syndrome suggest awake prone positioning as compared to supine positioning for non-intubated patients with COVID-19-related AHRF to reduce intubation (5). Since the COVID-19 pandemic awake prone positioning has become a medical standard therapy in the intensive care setting worldwide. However, to date there is insufficient data on the effect of APP in non-COVID-19 patients with AHRF. Furthermore, it is of importance that currently there is no evidence of the effect of APP of patients with non-COVID-19 AHRF. Due to its good tolerability and not too complex implementation in spontaneous breathing patients APP could be beneficial in patients with AHRF. Potentially, endotracheal intubation and need for mechanical ventilation and its concomitant side effects could be avoided.

Because of these underlying body of evidence, we hypothesize that APP in non-intubated patients with AHRF in the ICU reduces the need for tracheal intubation and the rate of potentially fatal disease course as compared with supine/semi-recumbent position.

7.2 Clinical Use

Currently PP is used as routine therapy for patients with ARDS and mechanical ventilation in moderate to severe severity. PP in patients who are spontaneously breathing gained attention during the COVID-19 pandemic and was proven to be safe in these patient population why it is now also used as routine medical therapy in the intensive care setting worldwide.

7.3 Preclinical Results

n/a

7.4 Cautions and Tolerability

7.4.1 Contraindications

There are absolute and relative contraindication to APP. Similar to prone positioning of mechanically ventilated patients, absolute contraindications include spinal instability or at risk of spinal instability and further relative contraindications include unstable fractures (especially facial and pelvic), anterior burns

(large ventral surface area) and open wounds, severe shock, recent tracheal surgery, and raised intracranial pressure. Contraindications are also listed in the study manual; the feasibility will be assessed by the treating physician on-site. If APP in an individual patient is possible is up to the discretion of the treating physician.

7.4.2 Special Warnings and Preventive Measures for the Treatment

7.4.2.1 Nerval compression injuries

An important complication of PP is nerve compression injuries, particularly when the prone position is adopted for longer periods of time. Brachial plexus injuries post prone position for patients undergoing IMV is common and well described in the literature. Fortunately, the incidence of brachial or ulnar injuries with in the awake patient is rare. In a case report, a 61-year-old who practiced nocturnal prone positioning for over 2 weeks noted decreased sensation and dysesthesia in his bilateral ulnar forearms and fourth and fifth digits, which resolved completely after 1.5 months without intervention (16). The ulnar nerve may be compressed at the elbow in the condylar groove between the olecranon and the medial epicondyle of the humerus. Flexion narrows the cubital groove by tightening the room and causes bulging of its floor. Advice to reduce the incidence of ulnar injury would include reducing elbow flexion of more than 90 degrees.

7.4.3 Side Effects

There are various potential side effects of PP. The most data stems from studies reporting PP in ARDS when patients are invasively mechanically ventilated. Side effects include accidental removal of endotracheal tube, loss of tubes that deliver fluids and medicines to your veins (peripheral or central venous catheter), hemodynamic instability (low blood pressure or arrhythmia), temporary decreases in oxygen levels, blockage of airway. In the study by Guerin et al following side effects were reported, which were all non-significant between the PP and standard of care group (except cardiac arrest) (3).

Side effects in patients with tracheal intubation and mechanical ventilation during prone position:

- Non-scheduled extubation, 25 events (10.9%)
- Mainstem bronchus intubation, 5 (2.2%)
- Endotracheal tube obstruction, 5 (2.2%)
- Hemoptysis, 12 (5.2%)
- Cardiac arrest, 31 (13.5%)
- Oxygen saturation by pulse oximetry < 85% or PaO₂ < 55 mm Hg > 5 minutes, 164 (71.6%)
- Heart rate < 30 beats.min⁻¹ > 1 minute, 27 (11.8%)
- Systolic blood pressure < 60 mmHg > 5 minutes, 48 (21.0%)

7.5 Rationale

Patients with AHRF are at risk for further worsening of respiratory function and need for oxygen supplementation or even more advanced non-invasive respiratory support or invasive mechanical ventilation if the clinical situation further worsens. Data show a benefit of prone position in invasive mechanical ventilated patients with moderate to severe ARDS. Further data support its benefit in COVID-19 patients with need for non-invasive mechanical ventilation. Since the COVID-19 pandemic APP use increased and became a standard medical therapy in ICUs worldwide. There are currently no RCTs for non-COVID-19 patients with AHRF.

Therefore, this investigator-initiated, prospective, randomized, open, blinded endpoint assessment (PROBE) interventional multi-center trial will investigate whether standard awake prone positioning compared to standard supine/semi-recumbent positioning can improve objective endpoints, relevant for prognosis in patients with AHRF.

Eligible patients will be randomized 1:1 to intervention arm or control arm. Patients enrolled to the interventional arm will receive standard therapy during course of hospital stay and additional standard awake prone positioning for 72h (targeted time in prone position 10 h/day (per 24 h period)) after randomization. Patients enrolled to the control arm will receive standard medical therapy in supine/semi-recumbent position. If patients have to be intubated and mechanically ventilated in both the interventional and control arm treatment should include standard ARDS therapy, including prone positioning in the case of moderate-severe ARDS.

7.6 Benefit- Risk Considerations

There is substantial need to improve therapeutic options in AHRF. Awake prone positioning and PP appears to be a safe and promising approach under the light of recent findings.

However, a considerable number of patients with AHRF and with or without APP will eventually need tracheal intubation and invasive mechanical ventilation. Patients with HFNC/NIV will be monitored closely clinically and with continuous vital sign monitoring will detect clinically worsening. An indication for endotracheal intubation won't be deferred. Based on the study hypotheses and previous studies in patients with COVID-19 we expect that there will be a lower rate of tracheal intubation and invasive mechanical ventilation which prevents complications associated with invasive mechanical ventilation.

Since the therapy is unblinded for both the patients and the supervising investigators, an unblinding procedure is not necessary. A Data Safety and Monitoring Board (DSMB) will be established to further minimise the risk for the patients.

Due to the fact that prone positioning is a standard manoeuvre in patients with AHRF/ARDS it can be defined as intensive care medical standard procedure. Therefore, no dedicated patient insurance will be needed.

The identifying data of patients will be kept securely at the participating sites. Clinical patient data will be stored central electronic data capture tool provided by the sponsor.

All aspects of the trial will be conducted in accordance with the Declaration of Helsinki principles, ICH-GCP rules and local laws. The study protocol will be submitted for ethical approval to the responsible ethics committees. All participants must provide written informed consent.

Primary aim of this study is to evaluate, if a standard APP strategy compared to a standard supine/semi-recumbent therapy leads to a reduction of all-cause mortality and/or rate of tracheal intubation in patients with AHRF. Furthermore, the safety and tolerability of APP in patients with AHRF will be assessed.

8 STUDY OBJECTIVES

Primary aim of the PROSA trial is to evaluate if a standard APP therapy strategy is superior to standard supine/semi-recumbent positioning therapy in reduction of all-cause mortality and/or tracheal intubation endpoints in patients with AHRF due to pneumonia.

All outcome measures were defined in accordance with highest scientific standards. In order to generate meaningful data, patient-related endpoints were chosen as the primary efficacy outcome. The secondary endpoints are also patient-related and can be precisely assessed.

8.1 Primary Objective

The primary objective of the PROSA-Study is to evaluate if the application of standard awake prone positioning in spontaneous breathing patients (defined as patients without invasive mechanical ventilation or extracorporeal respiratory support) with acute hypoxic respiratory failure due to pneumonia on the ICU is superior to standard supine/semi-recumbent positioning in reduction of the rate of tracheal intubation and / or all-cause mortality within 28 days after randomization. Furthermore, it should assess safety and tolerability of awake prone positioning in patients with acute hypoxic respiratory failure due to pneumonia on the ICU.

8.2 Primary Endpoints

Primary endpoint:

- Tracheal intubation and/or all-cause death within 28 days.

8.3 Secondary Endpoints

The secondary objectives are to compare the intervention treatment and control groups with respect to:

- All-cause mortality within 28 days
- Tracheal intubation within 28 days
- Duration of awake prone position (per day and total)
- days free from invasive mechanical ventilation or non-invasive ventilation at 28 days (defined as days alive without invasive/non-invasive ventilation)
- Rate of tracheotomy

- Differences in AHRF presumed origin
 - COVID-19
 - Influenza
 - Hospital acquired pneumonia
 - Community acquired pneumonia
 - Pneumonia in immunosuppressed individuals
- Device used
 - HFNO
 - NIV
 - CPAP
 - Combination of the above
- Effect on Oxygenation after awake prone positioning
 - Improvement of spO₂
 - Improvement in Horowitz Index
 - Respiratory Rate
- days alive and outside the intensive care unit at 28- days
- days alive and outside the hospital at 28- days
- hospital and intensive care unit length of stay
- Organ support
 - Rate and length of RRT
 - Need for vv-ECMO
 - Need for va-ECMO
- APP Related events

Primary safety endpoint

- Interruption of therapy due to intolerance to APP
- New treatment-related events (and changes in severity and frequency in these) related to APP

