	
Effect size assumed for power calculation: The sample size and power calculation are based on previous knowledge, assuming a 28-day event rate of the combined endpoint in the control group of 50%, and a reduction to 35% in patients with the experimental intervention. To account for possible imprecision regarding the assumptions, an adaptive design was chosen with one interim analysis after follow-up of 50% of the planned number of patients, in order to allow stopping early for futility or efficacy and to re-estimate the sample size. Based on these assumptions and for an overall one-sided type-one error of 2.5% and statistical power of 80%, 171 patients per group (342 overall) are planned to be enrolled to prove superiority. The maximum sample size will be restricted to 513 patients.
 
Safety: Rates of adverse events and serious adverse events will be tabulated by treatment group, according to type of event and system organ class. Safety endpoints for the APP group will be analysed descriptively (event rates with two-sided 95% confidence intervals).
 
Secondary endpoint(s): Treatment effects will be calculated with two-sided 95% confidence intervals and are of descriptive nature only. Secondary outcomes will be analysed depending on the scale type, corresponding to the primary analysis. Percentage of patients meeting key safety endpoints, as well as assessment of adverse events.

Safety:	To be randomized into the trial: n = 342 To be analysed: n = 342 – intention to treat analysis Adaptive sample size: n = 342 - 513
Number of Patients	
Note: adaptive sample size (see below for details)
 
Note: recruitment will be competitively among sites (currently 20 sites planned)

Table 1. STUDY SCHEDULES

Phase of study	Screening & Randomisation	Visit 2	Visit 3
Point in time	Day 1	Day 1-3	Day 28 (± 3 days)
Informed Consent	✓		
I/E Criteria	✓		
Medical History & Demographics	✓		
Vital Signs	✓	✓	
Routine laboratory values (blood count)	✓	✓	
Routine blood gas values	✓	✓	
Parameters of oxygenation and oxygenation therapy (HFNO, NIV, CPAP)	✓	✓	
Start of Intervention (Prone Positioning) therapy	✓	✓	
Endpoints	✓	✓	✓

Figure 1. Trial Flow

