9.3.3.3 Withdrawal of Patients from the Study

The following circumstances may lead to discontinuation of the study by an individual patient who will then be recorded as a drop-out. They include, but are not limited to the following issues:

- Withdrawal for personal reasons
- Adverse events necessitating withdrawal from the study
- Circumstances in which the health of the patient would be endangered upon continued participation in the study
- Lost-to follow-up

If a patient withdraws from the study at any time either at his or her request or at the Investigator's discretion, an "End-of-Study" visit should be performed and the "End-of-Study" eCRF section should be used to collect the relevant information. For the "End-of-Study" visit the same assessments should be made as for the discharge visit. The reason(s) for withdrawal must be recorded on the relevant page of the patient's eCRF and the patient's source data.

It is vital to obtain follow-up data for any patient withdrawn from the study because of an AE. Every effort must be made to undertake protocol-specific safety follow-up procedures. If a patient is discontinued due to an AE, the event should be followed up until resolution or until the event becomes chronic.

If a patient refuses to continue study procedures, the reason for refusal should be fully documented in the patient's source document and recorded in the study-specific eCRF.

It is the patient's right to withdraw from the trial without providing a reason. In this case, the source documents and the eCRF should document the reason for discontinuation as "withdrawal of consent".

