9.5.2.2 Study Examinations

Assessments are to be performed according to the schedule shown in Table 1 and depend on time-point of start of the intervention.

Safety will be evaluated by collecting reported adverse events at regular intervals throughout the study and by the assessment of vital signs, clinical laboratory parameters, ECGs, and adverse events.

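### The primary safety endpoint is defined by exposure to APP and attribution to it, so it cannot compare the arms; count the named harms in both arms instead

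*Protocol*

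**What the plan says.** Protocol section 8.3 names a primary safety endpoint with two components: "Interruption of therapy due to intolerance to APP" and "New treatment-related events (and changes in severity and frequency in these) related to APP". The synopsis, under Safety, gives the analysis: "Safety endpoints for the APP group will be analysed descriptively (event rates with two-sided 95% confidence intervals".

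APP-related events also appear as an item in the secondary endpoint list of section 8.3 and of the synopsis. That list opens with "The secondary objectives are to compare the intervention treatment and control groups with respect to".

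Other parts of the protocol bear on this:
- Section 9.4.1.2 excludes APP from control care. Rescue APP in controls is discouraged and recorded as a protocol violation.
- The synopsis and section 9.7.1.2.2.1 tabulate adverse events (AEs) and serious adverse events (SAEs) by treatment group, by event type and system organ class.
- Section 9.7.1.2.1.3 limits the safety set to patients who received any intervention, analysed as randomised. It does not say whether standard positioning counts as an intervention.
- Section 9.5.2.2 states "Safety will be evaluated by collecting reported adverse events at regular intervals throughout the study". It also relies on ECGs and ties assessments to Table 1. Table 1 has no AE row and no ECG row, only a general endpoints row at each visit.

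**The concern.** Safety and tolerability of APP is a stated objective (synopsis, objective ii; section 8.1). Both components of the endpoint chosen for it need APP exposure, and the second also needs a judgement that APP was the cause. This gives a rate in one arm with no reference.

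The listing of APP-related events as a between-arm outcome makes matters worse. With controls kept off APP, the control value is fixed near zero by definition. Any background event attributed to APP then counts as an excess, whether or not APP changed the true rate.

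The protocol gives a reason to expect background events. Section 7.4.3 says of an earlier trial in intubated patients that the "following side effects were reported, which were all non-significant between the PP and standard of care group (except cardiac arrest". That source does not give rates for awake patients, but it describes harms that also occur without proning.

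**Working it through.** **The plan's own figure.** The protocol gives no expected rate, precision or power for the safety endpoint. The only sample size is the efficacy one: 342, or 171 per arm (section 9.7.1.3), from 50% versus 35%, one-sided 0.025 and 80% power. The two-stage O'Brien-Fleming formula gives 336 in total with unpooled variance and about 171 per arm with pooled variance, so 171 per arm is a sound basis for the precision below.

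**Step 1: who can have an event.** In the APP arm, any proned patient can. In the control arm, only a patient given rescue APP against protocol can, and that patient stays in the control arm for analysis. The control count is therefore near zero by construction, though not strictly zero.

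**Step 2: what the endpoint yields as written.** It is a single-arm proportion with n = 171.
- Zero events: upper exact two-sided 95% limit = 1 − 0.025^(1/171) = 2.1%.
- Nine events (9/171 = 5.3%): exact (Clopper-Pearson) 95% CI 2.4% to 9.8%.

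Neither result can be set against a control rate.

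**Step 3: what happens if it is compared between arms.** Assume that a harm occurs in 10% of both arms (true difference zero), that a share *a* of APP-arm events is attributed to APP, and that no control receives rescue APP. The reported APP-arm rate is 10% × *a*.

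| Share attributed | Reported APP arm | Events (171 × rate) | Control | True difference |
|---|---|---|---|---|
| 25% | 2.5% | 4.3 | about 0% | 0 |
| 50% | 5.0% | 8.6 | about 0% | 0 |
| 75% | 7.5% | 12.8 | about 0% | 0 |

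Take the middle row as 9 events against 0. The difference is 5.3 points. A simple Wald half-width is 1.96 × √(0.0526 × 0.9474/171) = 3.3 points, so the interval runs from about 1.9 to 8.6 points. It excludes zero although APP did nothing. (The Wald interval is crude with an empty cell and serves only as illustration.)

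**Step 4: the same harm counted in both arms regardless of attribution.** For equal rates p in both arms, half-width = 1.96 × √(2p(1−p)/n).

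| Assumed background p | n = 171 per arm | n ≈ 256 per arm (maximum 513) |
|---|---|---|
| 5% | 1.96 × √(0.095/171) = 4.6 points | 3.8 points |
| 10% | 1.96 × √(0.18/171) = 6.4 points | 5.2 points |
| 20% | 1.96 × √(0.32/171) = 8.5 points | 6.9 points |

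With 171 per arm and 80% power (two-sided 0.05), the detectable increases are 5% to 13.8%, 10% to 20.9% and 20% to 33.4%. The trial is thus informative about moderate excesses of common harms. It is not informative about small increases in rare ones.

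**The case against.** The strongest reply is that the protocol already plans a comparison that needs no attribution: AE and SAE rates by treatment group. The data safety monitoring board also receives AE data, and SAE data by severity and causality (section 9.9). Mortality, intubation, renal replacement therapy and ECMO are compared between arms, and vital signs are taken at the Table 1 visits without restriction by arm. An APP-arm tolerability rate with a descriptive interval alongside such tables is a legitimate choice. All of this stands. A reader might infer that no between-arm safety estimate is possible; the documents do not support that.

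A reader might also infer that relatedness is judged by staff who know the arm. Sites are open and outcome assessors are blinded (section 9.4.3), but no section says who judges relatedness. The point does not need that inference: the endpoint fails as a comparison because it is defined by exposure, whoever makes the judgement.

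A third tempting reading is that follow-up is too short for nerve injury. Section 7.4.2.1 describes one case, "which resolved completely after 1.5 months without intervention", while Table 1 ends at day 28 (± 3 days). Section 9.3.3.3 extends follow-up only in this form: "If a patient is discontinued due to an AE, the event should be followed up until resolution or until the event becomes chronic". However, the case followed more than two weeks of nightly proning, against 72 hours here, and the same section calls such injuries rare in awake patients. That is too little to support a longer follow-up rule.

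The missing rows in Table 1 are a gap to reconcile, not evidence that adverse events go uncollected. Section 9.5.2.2 says they are collected, and the study manual and statistical analysis plan, which are not shown, may give the detail.

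**Conclusion.** The point holds in a limited form. The named primary safety endpoint is non-comparative and rests on attribution. Listing APP-related events as an outcome to compare between arms contradicts the APP-group analysis in the synopsis and would produce an excess by construction. Under the assumptions in the working (10% background in both arms, 25–75% attribution), that artefact is 2.5 to 7.5 percentage points with a true difference of zero. Background and attribution rates are assumptions, since the protocol gives none for awake patients.

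The trial can still compare harms through the AE and SAE table by arm. That table carries the comparative evidence on these harms. It would be firmer if the protocol said that controls are in the safety set and if Table 1 agreed with section 9.5.2.2. This is a worthwhile and inexpensive improvement. It does not affect the efficacy design.

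**What to change.** 1. Keep interruption for intolerance, labelled as an APP-arm tolerability measure with no between-arm comparison.
2. For the second primary safety component, and for APP-related events in the secondary list, count each harm the protocol already names: desaturation, hypotension or arrhythmia, loss of vascular access, pressure sore, nerve compression symptoms and cardiac arrest. Count them in both randomised arms from randomisation, by the same definitions, regardless of attribution.
3. Report each harm separately as a risk difference with a 95% CI. An any-event composite may be added but should not stand alone. Desaturation was recorded in 71.6% of the intubated prone patients cited in section 7.4.3 and could swamp the rarer harms.
4. State in section 9.7.1.2.1.3 that control patients belong to the safety set.
5. Reconcile Table 1 with the AE and ECG collection in section 9.5.2.2.

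**Cost.** Sites complete one short eCRF checklist in both arms, and the report gains one table. Sample size, treatment and the primary efficacy analysis are unchanged. Because sites are open, ascertainment bias is reduced by a common checklist but not removed.
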